4.0 STUDY ENDPOINTS

4.1 Effectiveness Endpoints

4.1.1 Primary Effectiveness Endpoint

The primary effectiveness endpoint is the change in medication-free mean diurnal IOP from baseline at 12 months (i.e. medication-free mean diurnal IOP at 12 months – medication-free mean diurnal IOP at baseline). The medication-free mean diurnal IOP (i.e. average of three medication-free IOP's measured at three different time points) will be calculated for each subject. For each subject, a negative change in mean diurnal IOP value means a reduction; a positive value means an increase.

Criteria for Failure to Respond

The medication-free mean diurnal IOP at 12 months will be imputed for subjects who meet the following criteria:

- IOP persistently below 6mmHg (defined as an intraocular pressure below 6mmHg that is present on two consecutive follow-up visits after the three month visit),
- underwent secondary IOP lowering interventions to control IOP (e.g., laser trabeculoplasty, trabeculectomy, shunt or valve placement, iridotomy/iridectomy) prior to the 12-month visit,
- post-operative introduction of an oral carbonic anhydrase inhibitor,¹
- no diurnal IOP data collected from the available Month 12 visit,
- underwent other secondary surgical interventions (SSI) that could affect IOP, or
- use of ocular hypotensive medication within 4 weeks of the Month 12 washout visit²

¹ Does not include use in the perioperative period

² If the study subject fails to remember not to use ocular hypotensive medication for the study eye per the required washout period prior to this visit, they can be reinstated to washout and return for a 12 month washout IOP visit as long as it falls within the specified visit window.

For subjects who meet any of the criteria above, the medication-free mean diurnal IOP at 12 months will be imputed by the mean washout (i.e. medication-free) diurnal IOP at baseline.

It is expected that the follow-up rate will be better than 90% at 12 months postoperatively. Therefore, the primary analyses for the primary and secondary effectiveness endpoints will be based on the available medication-free mean diurnal IOP data at 12 months with the imputation described above. For sensitivity analyses, imputations of the missing 12-month medication-free diurnal IOP will be performed for the subjects that do not meet the criteria above and are discontinued prior to the 12-month visit (Section 9.4.3).

The mean of change in medication-free mean diurnal IOP from baseline at 12 months will be compared between the VISCO360 group and control group. The corresponding statistical hypotheses are as follows:

$$H_0: \mu_c - \mu_v = 0 \text{ versus } H_A: \mu_c - \mu_v > 0$$

The μ_v and μ_c are the mean change in medication-free mean diurnal IOP changes from baseline at 12-month for the VISCO360 group and control group, respectively. The VISCO360 group will be concluded to be superior to the control group in reducing the IOP if the null hypothesis (H_0) is rejected based on one-sided significance level of 0.025.

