7.2 EXCLUSION CRITERIA

All criteria apply to the study eye unless otherwise noted and both eyes of a single subject need not be eligible):

1. Phakia or aphakia
2. Posterior Capsular Opacification graded as moderate or severe using the sample images provided in Appendix 1. In this case, a laser capsulotomy can be performed and the subject screened again a minimum of two weeks following the capsulotomy.
3. Presence of Anterior Chamber IOL (ACIOL)
4. History of complicated cataract surgery (e.g. vitreous loss, sutured IOL, decentered IOL, etc.)
5. Pre-existing IOL instability
6. Diagnosis of acute angle closure, traumatic, congenital, malignant, uveitic, pseudoexfoliative, pigmentary or neovascular glaucoma
7. Inability to properly visualize angle (due to corneal scar, edema, etc.)
8. Abnormal angle anatomy as determined by gonioscopy (e.g. peripheral anterior synechiae, rubeosis or other angle abnormalities)
9. Conditions associated with elevated episcleral venous pressure such as active thyroid orbitopathy, cavernous sinus fistula, Sturge-Weber syndrome, orbital tumors, orbital congestive disease.
10. The subject would be at significant risk by washout of ocular hypotensive medication including any of the following:
 - Unmedicated IOP after washout period is expected to exceed upper limit of 36.0 mmHg at Baseline visit
 - Presence of afferent pupillary defect in either eye
 - C:D ratio ≥ 0.9 in either eye
 - Requiring oral medications (e.g., acetazolamide) for IOP control in either eye

- Evidence of advanced glaucoma in either eye by 24-2 SITA Standard Humphrey visual field defined as mean deviation (MD) of -12.00 or worse and at least one of the following: (a) On PD plot, greater than or equal to 75% of points depressed below the 5% level and greater than or equal to 50% of points depressed below 1% level; or (b) At least 50% of points (i.e., 2 or more) within central 5 degrees with sensitivity of < 0dB on the dB plot; or (c) Points within the central 5 degrees of fixation with sensitivity < 15dB in both hemifields on the dB plot.
- Visual field defects threatening fixation in either eye defined as any (1 or more) point(s) within the central 5° depressed below the 5th percentile on PD plot unless this/these points are >25 dB on Threshold Values (decibel) plot.

11. Subjects with Snellen best-corrected visual acuity worse than 20/80 in either eye.
12. At Baseline visit, subject has not completed appropriate medication washout, if applicable

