8.7 WASHOUT

Subjects who meet all screening eligibility criteria will be instructed to discontinue their ocular hypotensive medication regimen in the study eye only, and to return for a baseline visit after completing the appropriate washout period. Glaucoma medication discontinuation can be staged so that the pressure increase duration is minimized to the greatest possible extent during the washout period.

If the subject does not currently take any glaucoma medication, the Baseline Exam can be scheduled as soon as two (2) days after completing the Screening Exam.

All subjects on ocular hypotensive medication(s) at Screening and Month 12 will be instructed to undergo a washout prior to the Baseline/Month 12 postoperative visit. If a subject cannot be washed out of their ocular hypotensive medications, the medical monitor will review the subject records and the decision in a masked fashion. If the study subject fails to remember not to use ocular hypotensive medication for the study eye per the required washout period, they can be re-instructed to washout and return for a 12-month washout IOP visit as long as it falls within the specified visit window.

The minimum wash-out periods are specified in **Table 1** below. Note: The maximum washout period is 6 weeks. Therefore, if the surgery/SLT procedure cannot be scheduled within one week of the end of the washout period, the subject should be restarted on glaucoma medication until the Day 0 visit.

TABLE 1: OCULAR HYPOTENSIVE MEDICATION WASHOUT PERIODS

Brand Name/Chemical Name	Minimum washout period
Carbonic Anhydrase Inhibitors	
Diamox® (Acetazolamide) – oral Rx	5 days
Neptazane® (Methazolamide) – oral Rx	5 days
Azopt® (Brinzolamide)	5 days
Trusopt® (Dorzolamide Hydrochloride)	5 days
Alpha Adrenergic Agonist	
Alphagan® (Brimonidine)	14 days
Iopidine® (Apraclonidine Hydrochloride)	14 days
Beta Blockers	
Betagan® (Levobunolol Hydrochloride)	28 days
Betoptic® (Betaxolol Hydrochloride)	28 days
OptiPranolol® (Metipranolol)	28 days
Timoptic/Betimol® (Timolol Maleate)	28 days
Prostaglandin Analogs	
Lumigan® (Bimatoprost)	28 days
Travatan® (Travoprost)	28 days
Xalatan® (Latanoprost)	28 days
Zioptan® (Tafluprost)	28 days
Combined Medications	
Combigan® (Brimonidine Tartrate/Timolol Maleate)	28 days
Cosopt® (Dorzolamide Hydrochloride/ Timolol Maleate)	28 days
Simbrinza® (Brinzolamide/Brimonidine Tartrate)	28 days
Other	Contact Sponsor

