8.2.5 Washout

For subjects taking hypotensive medications at screening and 12 months after surgery, the minimum wash-out periods are specified in the study protocol.

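### The Month 12 failure rule looks back a flat 4 weeks, but Table 1 requires only 5 or 14 days for two drug classes, so some correctly washed-out subjects are scored as failures

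*SAP*

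**What the plan says.** **The failure rule.** SAP 4.1.1 lists among its criteria for failure "use of ocular hypotensive medication within 4 weeks of the Month 12 washout visit". Protocol 6.1 has the same criterion in its lists for the primary and the secondary endpoint. It makes no distinction by drug class. A subject who meets it has the baseline washout IOP entered as the 12-month value, so the primary-endpoint change is zero. SAP 4.1.2 makes the same subject a non-responder.

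**The washout rule.** Under Protocol 8.7, subjects on medication at Screening and Month 12 "will be instructed to undergo a washout prior to the Baseline/Month 12 postoperative visit". Table 1 in that section gives minimum periods by drug. SAP 8.2.5 confirms that they apply at both times: "For subjects taking hypotensive medications at screening and 12 months after surgery, the minimum wash-out periods are specified in the study protocol". Protocol 8.7 also sets an upper limit: "The maximum washout period is 6 weeks".

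**The baseline standard.** Exclusion criterion 12 in Protocol 7.2 reads "At Baseline visit, subject has not completed appropriate medication washout, if applicable". At baseline, then, a washout that meets Table 1 is enough.

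**The concern.** The primary endpoint is the difference between two medication-free IOP values, but the plan uses two definitions of medication-free. After a 7-day dorzolamide washout, the baseline IOP is valid. The Month 12 IOP after the same 7 days is discarded and replaced by that baseline value.

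Two eyes with the same response to the procedure can therefore be scored differently because one was on latanoprost and the other on dorzolamide, or because two sites chose different stopping dates. Both effectiveness endpoints inherit the problem. An analyst who follows the rule discards valid data; one who does not departs from the written plan after the data are in.

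**Working it through.** **1. The two rules side by side.** Four weeks is taken as 28 days, with a last dose fewer than 28 days before the visit triggering failure.

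| Class (Protocol Table 1) | Minimum washout | Compliant but scored as failure |
|---|---|---|
| Topical carbonic anhydrase inhibitors | 5 days | days 5–27 (28 − 5 = 23 days) |
| Alpha agonists | 14 days | days 14–27 (28 − 14 = 14 days) |
| Beta blockers, prostaglandin analogs | 28 days | none |
| All listed combinations, including brinzolamide/brimonidine | 28 days | none |

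Oral carbonic anhydrase inhibitors are a separate failure criterion and are not part of this conflict.

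**2. Does anything in the text resolve it?** The footnote to the criterion lets a subject who forgot the washout repeat it within the visit window. It refers to the washout that was required of the subject, which is the Table 1 period, so a compliant subject has nothing to repeat. The imputation sensitivity analyses described in SAP 4.1.1 cover only subjects who do not meet the failure criteria. SAP 7.3 keeps the baseline imputation in both the mITT and PP analyses. SAP 9.4.3 is not readable in the public version, so nothing is claimed about it.

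**3. Can such subjects exist?** Yes. Protocol 8.8 re-introduces the drug classes used before the procedure, and its order includes alpha agonists and carbonic anhydrase inhibitors.

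**4. The plan's sample sizes reproduce.**
- Primary (SD 5, difference 2 mmHg, one-sided 0.025): noncentral-t power is 0.8993 at 132 per arm and 0.9015 at 133, giving the stated 133. Then 133/0.9 = 147.8, so 148 per arm and 296 in total.
- Secondary (0.50 vs 0.70): the continuity-corrected formula gives the stated 134, and exact one-sided Fisher power there is 0.905. Then 134/0.9 = 148.9, so 149 per arm and 298 in total. The figure reproduces with a VISCO360 rate of 0.70, not the printed 0.2, so 0.70 is used below.

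**5. Illustration of size.** The affected share f is not in the documents; 2%, 5% and 10% are assumed. True mean reductions are assumed to be 5.5 mmHg for SLT (the cited SLT study) and 7.5 for VISCO360 (5.5 plus the design difference of 2), with SD 5 and 134 per arm.

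*Case A: affected eyes have their arm's average reduction μ.* The mean after scoring is (1 − f)μ and the variance is (1 − f)·25 + f(1 − f)μ². At f = 5%:
- Means: 0.95 × 7.5 = 7.125 and 0.95 × 5.5 = 5.225; difference 1.90.
- Variances: 23.75 + 0.0475 × 56.25 = 26.42 and 23.75 + 0.0475 × 30.25 = 25.19.
- Power: 86.2%.

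*Case B: affected eyes truly fall by 2 mmHg in both arms, with overall arm means held at 7.5 and 5.5.* The unaffected mean is u = (μ − 2f)/(1 − f), the mean after scoring is (1 − f)u, and the variance is (1 − f)·25 + f(1 − f)u². At f = 5% the means are 7.4 and 5.4. The difference stays at 2.00, and only the variance rises.

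For the secondary endpoint, Case A multiplies both response rates by (1 − f). Case B assumes that 20% of affected eyes truly respond, so 0.2f is subtracted from each rate.

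| Equal f in both arms | Primary, A | Primary, B | Secondary, A | Secondary, B |
|---|---|---|---|---|
| 0 | 90.4% | 90.4% | 90.5% | 90.5% |
| 2% | 88.8% | 89.9% | 89.1% | 90.4% |
| 5% | 86.2% | 89.3% | 86.8% | 90.4% |
| 10% | 81.5% | 88.1% | 81.7% | 90.2% |

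**6. Unequal shares.** The shift in the estimated difference is f_SLT·m_SLT − f_VISCO·m_VISCO, where m is the true mean reduction in affected eyes.
- If m is the same in both arms, each percentage point of imbalance shifts the difference by 0.01 × 2 = 0.02 to 0.01 × 5.5 = 0.055 mmHg.
- With arm-average reductions, 5% SLT and 2% VISCO360 gives 0.98 × 7.5 − 0.95 × 5.5 = 2.125 mmHg. The reverse gives 0.95 × 7.5 − 0.98 × 5.5 = 1.735 mmHg. The true difference is 2.

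**The case against.** **The rules can be satisfied together.** Table 1 gives minimums. A 28-day stop for every drug meets Table 1, the 6-week maximum, the Day 330–420 window and the failure rule, and a uniform 4-week interval is a defensible, stricter definition. This is correct, but nothing in the available text tells sites to do it. Protocol Table 2, the visit schedule, is not in that text, so an instruction there cannot be ruled out.

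**The group is small.** A subject must be on medication at Month 12, have a short-washout drug as the last one stopped, and stop it fewer than 28 days before the visit. Prostaglandins come first in the re-introduction order and need 28 days. Staged stopping would widen the group, but Protocol 8.7 mentions it only for the baseline washout. This stands.

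**These eyes have mostly responded poorly.** The standard rescue trigger in Protocol 8.8 is IOP of at least 21 mmHg and no more than 20% below the preoperative medicated value, at two consecutive visits. Case A is therefore pessimistic. That stands, and Case B is given for that reason. It does not justify replacing a measured value with an imputed one.

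**No direction of bias is shown.** This also stands. Equal shares mainly dilute the difference, which is conservative for superiority, and the documents give no reason to expect imbalance between arms.

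**Conclusion.** The concern holds. Followed as written, the plan scores some subjects who met the protocol's washout requirement as failures on both effectiveness endpoints, after accepting the same washout at baseline. The conflict lies within the protocol as well as between protocol and SAP.

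It is confined to topical carbonic anhydrase inhibitors and alpha agonists, and its effect is probably small. At an assumed equal share of 5%, primary power falls from 90.4% to between 86.2% and 89.3%, and secondary power from 90.5% to between 86.8% and 90.4%, depending on how well affected eyes truly respond. These figures rest on the assumed shares and reductions and do not predict the trial's result. The wording mismatch needs no such assumptions. It should be corrected because it touches both endpoints and costs little to remove.

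**What to change.** In both Protocol 6.1 lists and in SAP 4.1.1, change the look-back from 4 weeks to the Table 1 washout period for the agent concerned, counted back from the Month 12 washout visit. For agents under Other in Table 1, use the period the sponsor gave the site. SAP 4.1.2 follows automatically because it refers to 4.1.1.

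The change alters no washout length and leaves the rule as it is for every 28-day drug. The protocol wording goes through the modification route in Protocol 8.13, with IRB review as needed. The SAP wording should be amended before database lock under SAP 1.0. No patients, visits or procedures are added.

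The alternative is to instruct sites to use 28 days for every agent before the Month 12 washout visit. That leaves the endpoint wording alone, but it adds up to 23 days off a topical carbonic anhydrase inhibitor, or 14 days off an alpha agonist, beyond the Table 1 minimum. It would also make the Month 12 standard stricter than the one accepted at baseline, so tying the rule to Table 1 is preferable.

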8.10 WITHDRAWAL CRITERIA

All subjects have the right to withdraw at any point during the treatment without prejudice. The investigator can discontinue any subject at any time if continued participation in the study would result in harm to the subject. All efforts should be made by the investigator to retain the patient in the study. If a subject withdraws prematurely from the study, a genuine effort must be made to determine the reason(s) the subject discontinued the study. The reason must be recorded in the subject's file and on the End of Study Form and faxed to Sight Sciences, Inc. and the CRO (Sierra Clinical Services).

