13.0 MEDICAL MONITOR

An independent Medical Monitor will be used in the study. The Medical Monitor will not be an investigator in the study. The Medical Monitor will be a certified ophthalmologist with glaucoma specialization. The Medical Monitor will review adverse events and determine if the appropriate action have or are being taken. If a subject cannot be washed out of their ocular hypotensive medications, the medical monitor will review the subject records and the decision in a masked fashion.

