6.0 SAMPLE SIZE CALCULATION

The sample size for the primary effectiveness endpoint and the corresponding statistical hypotheses described in Section 4.1.1 is based on the following assumptions and criteria.

- The standard deviation of change in mean diurnal IOP from baseline at 12 months is assumed to be 5.0 mmHg. Per Seymenoglu³, the mean and standard deviation (SD) of the change in IOP from baseline to 12 months was 5.5 mmHg \pm 3.8 mmHg for the pseudophakic eyes with SLT, without additional medications, without SLT retreatments, and without any glaucoma-related secondary surgical intervention. Since the study will evaluate the change in the mean diurnal IOP from baseline after washout to 12 months after washout, the SD of the endpoint is expected to be larger than the published SD of 3.8 mmHg. An SD of 5 mmHg is assumed for the study.
- Significance level is 0.025 (one-sided) and statistical power is 90% at a true mean difference of 2 mmHg.
- Two-sample *t*-test will be used.
- A yearly dropout rate of 10% is considered.
- The randomization ratio for the study is 1:1.

Based on the criteria above, the 12-month sample size for the primary effectiveness endpoint and corresponding statistical hypotheses are **133** VISCO360 and **133** control subjects at 12 months. With the yearly dropout rate of 10%, approximately **296** subjects (**148** VISCO360 and **148** controls) should be randomized.

The sample size calculation for the secondary effectiveness endpoint and the corresponding statistical hypotheses described in Section 4.1.2 is based on the following assumptions and criteria:

³ [name] and [name] (2015). Efficacy of Selective Laser Trabeculoplasty in Phakic and Pseduphakic Eyes. J. Glaucoma, 2015;24:105–110.

- The 12-month IOP response rates for the control group (p_c) is estimated are estimated to be 0.5. Per Seymennoglu, the 12-month IOP response rate was 0.62 for the pseudophakic eyes with SLT, without additional medications, without SLT retreatments, and without any glaucoma-related secondary surgical intervention. Due to the requirement of medication washout in this study, it is expected that the 12-month response rate for the control group of this study is lower than the published 0.62. Therefore, a 12-month response rate of 0.50 is assumed for the control group.

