8.3 Handling of Missing or Incomplete Data

8.3.1 Missing Primary and Secondary Effectiveness Outcomes

For the primary and secondary effectiveness endpoints, the imputed values described in Sections 4.1.1 and 4.1.2 will be performed for the missing endpoints.

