9.4 Effectiveness Endpoints Analyses

9.4.1 Primary Analysis for Primary Effectiveness Endpoint

The primary analysis of the primary effectiveness objective described in Section 4.1.1 will be based on the mITT population. The medication-free mean diurnal IOP change from baseline at 12 months will be calculated for each study eye. As described in Section 4.1.1, for subjects meeting the criteria listed in Section 4.1.1, their 12-month medication-free mean diurnal IOP will be imputed by the baseline medication-free diurnal IOP. In order to assess the pattern of the distribution, box-plots will be prepared for the medication-free mean diurnal IOP and its change from baseline for each of the two study groups.

The descriptive statistics (such as mean, standard deviation, median, minimum, and maximum) of the medication-free mean diurnal IOP and the change from baseline and the 95% confidence interval of the mean will be calculated for each of the two study groups. A two-sample t-test with a one-sided significance level of 0.025 will be used to test the statistical hypotheses described in Section 4.1.1. The two-sided 95% confidence interval based on the t-distribution will also be provided for the mean difference in the medication-free mean diurnal IOP between the two study groups.

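### Subjects who leave before the Month 12 visit without meeting a failure criterion are left out of the deciding analysis, even when they leave for poor IOP control, while comparable subjects who stay are scored as failures

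*SAP*

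**What the plan says.** SAP 4.1.1 lists six criteria under which baseline IOP replaces the 12-month value, so that the change is zero:

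- persistent IOP below 6 mmHg
- a secondary IOP-lowering intervention
- an oral carbonic anhydrase inhibitor after the perioperative period
- no diurnal IOP from the available Month 12 visit
- other surgery that could affect IOP
- hypotensive medication within 4 weeks of the Month 12 washout visit

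Beyond that imputation, "the primary analyses for the primary and secondary effectiveness endpoints will be based on the available medication-free mean diurnal IOP data at 12 months". For sensitivity only, "imputations of the missing 12-month medication-free diurnal IOP will be performed for the subjects that do not meet the criteria above and are discontinued prior" (that is, before the Month 12 visit). SAP 4.1.2 repeats the rule for the responder endpoint, with the same criteria scored as non-response. The closing paragraph of SAP 7.3 repeats it for the mITT and per-protocol populations, and SAP 7.2 makes mITT the deciding population. Protocol 6.1 carries the same six criteria and does not say how discontinued subjects are handled.

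On leaving the study, Protocol 8.10 says: "The investigator can discontinue any subject at any time if continued participation in the study would result in harm to the subject". Subjects may also leave of their own accord. The reason goes on the End of Study Form. On washout, Protocol 13.0 provides for a review under masking: "If a subject cannot be washed out of their ocular hypotensive medications, the medical monitor will review the subject records and the decision in a" (the sentence ends by requiring masking); Protocol 8.7 says the same. No such review is stated for withdrawals.

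**The concern.** Two of the six criteria can be met only by someone who reaches Month 12. Topical rescue medication, which Protocol 8.8 allows, is not itself a criterion. Consider a subject with inadequate IOP control on topical rescue. Kept in the study and still on medication at Month 12 without a washed-out diurnal IOP, this subject counts as a failure. If the same subject discontinues at Month 8, no criterion is met and the subject leaves both deciding analyses.

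Exit for poor IOP control carries information about the outcome. The trial is single-masked, Protocol 8.2.1 seeks to mask the subject only until the procedure, and surgery and laser are visibly different. The masked tonometer reader protects the measurement but not the decision to leave. If such exits are more frequent in one arm, that arm loses failures and looks better than the plan's own failure logic would make it. Depending on the arm, this could produce a false finding of superiority or hide a true one.

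**Working it through.** **The plan's own figures.** SAP 6.0 gives the inputs: "Significance level is 0.025 (one-sided) and statistical power is 90% at a true mean difference of 2 mmHg"; "An SD of 5 mmHg is assumed for the study". SAP 9.4.1 gives the test: "A two-sample t-test with a one-sided significance level of 0.025 will be used".

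- Primary: n = 2 × (1.960 + 1.282)² × 5² / 2² = 131.3, so 132 per arm by the normal approximation. The noncentral t gives power 0.8993 at 132 and 0.9015 at 133, so 133. Then 133 / 0.9 = 147.8, so 148 randomized.
- Secondary: 0.70 v 0.50 with a continuity correction gives 134 per arm (exact Fisher power 0.905). Then 134 / 0.9 = 148.9, so 149 per arm, 298 in all. (SAP 6.0 prints the VISCO360 rate as 0.2; 134 reproduces only with 0.7, a wording slip that does not matter here.)

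The figures reproduce. Dividing by 0.9 treats dropouts as removed, which agrees with the available-data rule. The planned loss is 0.10 × 298 = 29.8, about 30 subjects.

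**Simple illustration.** Assumptions: mean reduction 5.5 mmHg in analysed subjects (the published SLT figure cited in SAP 6.0), SD 5, 134 per arm, excluded failures worth zero change, all in the VISCO360 arm, and no true difference once those failures are counted.

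- SE = 5 × √(2/134) = 0.611
- Shift = 5.5 × share excluded
- One-sided error = 1 − Φ(1.96 − shift/SE)

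| Excluded failures, VISCO360 v SLT | Shift (mmHg) | One-sided error |
|---|---|---|
| 2% v 0% | 0.11 | 0.038 |
| 5% v 0% | 0.275 | 0.066 |
| 10% v 0% | 0.55 | 0.145 |

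**Second illustration.** Assumptions: 149 per arm, 15% would-be failures in each arm, and the rest with mean change m = −5.5 (range −4 to −7) and SD 5. If a share f of the arm leaves from among the failures, the remaining failure share is k = (0.15 − f)/(1 − f). The analysed mean is (1 − k)m, the variance (1 − k) × 25 + k(1 − k)m², and the number analysed 149(1 − f).

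- 10% v 5%: k = 0.0556 and 0.1053; means −5.194 and −4.921; shift 0.27 mmHg (0.20 to 0.35); error 6.6% (5.2% to 8.1%).
- 10% v 0%: means −5.194 and −4.675; shift 0.52 mmHg (0.38 to 0.66); error 13.8% (9.5% to 18.7%).
- 10% v 10%: no shift; error 2.5%.

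For the responder endpoint with a true rate of 0.50 in both arms, 10% v 5% gives 0.50/0.90 = 0.556 v 0.50/0.95 = 0.526 and an error of 5.6%. At 10% v 0% it is 12.6%. With no withdrawals Fisher's test runs at 2.1%.

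**Power if discontinued subjects score zero change.** This is the extreme in which all 10% of dropouts do so.

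- Difference = 0.9 × 2 = 1.8 mmHg
- SLT variance = 0.9 × 25 + 0.1 × 0.9 × 5.5² = 25.22
- VISCO360 variance = 0.9 × 25 + 0.1 × 0.9 × 7.5² = 27.56
- Pooled SD = √26.39 = 5.14

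At 149 per arm power is 85% (83% to 87% for an SLT reduction of 7 to 4 mmHg), against 90% under the available-data rule. Restoring 90% would take about 173 per arm (163 to 185). Responder endpoint: 0.63 v 0.45, power 86%.

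**The case against.** The strongest reply is that the gap is narrow and the plan works to keep it small. Protocol 8.10 asks investigators to make every effort to retain subjects and limits investigator withdrawal to harm. Protocol 8.8 lets poor control be treated within the study, and Protocol 10.4 keeps subjects who need further glaucoma surgery in follow-up. Anyone who already had a secondary intervention, other relevant surgery, an oral carbonic anhydrase inhibitor or persistent IOP below 6 mmHg remains a failure after leaving. ITT and imputation analyses are planned as sensitivity analyses. All of this stands and limits how many subjects are affected. It does not change the deciding rule for the rest.

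Three stronger readings are tempting and are not supported.

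- A reader might infer that withdrawing a subject who cannot wash out at Month 12 turns a failure into an exclusion. Under Protocol 8.9 a medicated subject attends the Month 12 visit first and returns later for the washout visit. If washout then fails, there is no diurnal IOP from an attended Month 12 visit, and the subject is a failure even if withdrawn afterwards. Protocol 8.7 can be read as washout before the visit, but 8.9 is the explicit schedule.
- A reader might take SAP 8.3.1, "the imputed values described in Sections 4.1.1 and 4.1.2 will be performed for the missing endpoints", as contradicting 4.1.1. It refers back to 4.1.1 and 4.1.2 and leaves their rule unchanged.
- A reader might see a conflict between the follow-up of better than 90% expected in SAP 4.1.1 and the 10% dropout allowance. An expectation slightly better than a planning allowance is ordinary.

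The content of SAP 9.4.3 is not visible in the public text, so nothing is claimed about the quality of the sensitivity imputation.

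**Conclusion.** The point holds for subjects who discontinue before the Month 12 visit and meet none of the six criteria. Those who leave for inadequate IOP control are omitted from the deciding analyses, although the plan treats a comparable outcome as failure in subjects who stay. That the decision to leave is unmasked is an inference from the design, since no masked review of it is stated.

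The direction of any bias is unknown, and its size depends on how unequal such exits are between arms, for which the documents give no figure. The 10% v 0% case is extreme: every planned dropout in one arm would be an excluded failure and none in the other. The 2% and 5% rows, or 10% v 5%, better show what modest imbalance does: an error of roughly 0.04 to 0.07 in place of 0.025 if the exits fall in the VISCO360 arm. The gap should be closed, but it does not invalidate the design.

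**What to change.** Add one criterion to SAP 4.1.1 and 4.1.2 and to Protocol 6.1: discontinued before the Month 12 visit because of inadequate IOP control or need for further glaucoma treatment. Such subjects are then scored as zero change and as non-responders, like the other failures. Use the exit reason already recorded on the End of Study Form, and have it classified masked to arm before database lock. Keep the available-data result as a sensitivity analysis.

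Protocol 8.7 and 13.0 should be reconciled with 8.10 on how subjects who cannot wash out are handled. The clinical decision is for the sponsor.

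The cost is wording and a masked classification step. There is some loss of power, which should be restated. It is bounded by the extreme case worked above, about 85% at 149 per arm instead of 90%, and will be smaller because only IOP-related exits are rescored. The criterion also depends on exit reasons being specific enough to classify.
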